8.1 EFFICACY ASSESSMENTS

The study will have the following visits/calls: (1) telephone screening; (2) in person-screening and baseline study visit; (3) telephone calls for titration; (4) Follow up visits at months 6, 12, 18 months; (5) monthly calls between 6-month visits; (6) Brain Magnetic Resonance Imaging (MRI) at baseline and month 18. Primary and secondary clinical (non-MRI) efficacy data will be collected at baseline and the 6-month visits. Secondary MRI efficacy data will be collected at baseline and 18 months. The following is a brief description of these visits and the assessments included in these visits.

1. Telephone screening. We propose a 2-tier approach for screening, including telephone pre-screening followed by in-person screening. Telephone screening includes questions about inclusion and exclusion criteria including demographics, social history, medical history, contraindications to metformin, and medications. Study sites have the option of conducting a telephone cognitive screen such as the TICS to exclude persons with normal cognition.

Only persons who meet inclusion criteria and do not meet exclusion criteria are invited for in-person screening/baseline visit.

2. In-person screening and baseline study visit. In-person screening includes written informed consent, demographics, anthropometric measurements (height, weight, waist and hip circumference), vital signs (blood pressure and heart rate), EKG, laboratory tests (thyroid stimulating hormone [TSH], rapid plasma reagin [RPR], vitamin B12, complete blood count [CBC], basic metabolic panel [BMP], hepatic panel, lipid panel, and HbA1c), the neuropsychological battery, and a COVID-19 questionnaire. At the time of screening the tester will complete other assessments if the participant meets the neuropsychological criteria for MCI. All evaluations will be recorded in the eCRF, as applicable. If the participant meets all the inclusion criteria and has no exclusion criteria, the participant will be randomized and mailed a randomization kit with IP.

3. Telephone calls for titration. There will be 4 calls, one at the beginning of titration (one tablet a day), and 3 more calls every 10 days when the dose is increased by one tablet a day. During these calls, adverse events and tolerance will be documented.

4. Follow-up visits at months 6, 12, and 18 will include data collection on anthropometric measurements (height, weight, waist and hip circumference), vital signs (blood pressure and heart rate), brief neurologic exam laboratory tests (vitamin B12, CBC, BMP, hepatic panel, lipid panel, and HbA1c), the neuropsychological battery, and the COVID-19 questionnaire. Adverse events and compliance will also be recorded. At the time of screening the tester will complete other assessments if the participant meets the neuropsychological criteria for MCI. All evaluations will be recorded in the eCRF, as applicable.

5. Monthly calls between 6-month visits: adverse events and compliance will be recorded
6. Brain MRI will be conducted at baseline and 18 months.
7. Amyloid PET will be conducted at baseline and 18 months.
8. Tau PET will be conducted at baseline and 18 months.
9. Plasma AD biomarkers will be measured in stored plasma from the 4 main visits (baseline and months 6, 12, and 18).

The following is a description of all assessments:

Capacity to consent

We will use the University of California, San Diego Brief Assessment of Capacity to Consent (UBACC)¹³⁵ to assess capacity in the study. The UBACC is a 10-item scale that assesses understanding and appreciation of the information related to a research protocol. The UBACC will be available in English and Spanish. It is important to point out that the study excludes participants with dementia at baseline (determined by a clinical dementia rating summary score of 1 or higher). Thus, all participants have in principle a cognitive status that allows for capacity to consent at baseline. There are two situations in which we will assess capacity to consent with the UBACC.

- Throughout the study if the study staff appreciate that the participant does not comprehend the study information during the consent process regardless of cognitive status. At baseline, lack of capacity to understand the study will constitute a reason for exclusion. During follow-up assessments, determination of lack of capacity to consent will lead to the need for a legal authorized representative to consent after the participant provides assent to participate.
- During follow-up, if the participant develops dementia, indicated by a clinical dementia rating summary score of 1 as determined in the previous follow-up assessment. If the participant demonstrates capacity, he/she may consent; if the participant lacks capacity but wants to continue participation, a legally authorized representative will need to provide consent after the participant's assent. It is important to point out that this approach respects the participant's decision at baseline to participate in the study, when he/she had the capacity to consent.

Participants will be given three trials to respond to the UBACC. If after three trials they do not have a perfect score, they will be determined to lack capacity to consent. The determination of lacking capacity to consent will lead to exclusion at baseline, and to the need for a legally authorized representative to provide consent during follow-up. We expect that the contingencies described above will occur in less than 5% of the participants in the study, who will have mild cognitive impairment at baseline.

Medical history, medications

Detailed medical, surgical, and psychological history, and all medications utilized, including a judgment as to whether they affect cognition (positively or negatively) will be collected at baseline. Psychiatric history, current and past history of depression, current anxiety, alcohol and other substance use, head injury, hypertension, cardiac disease, thyroid disease, other major medical conditions, and surgery are evaluated at the baseline visit. A full medical history will be obtained only at the baseline visit. Any report of events, or side effects will prompt a full history and physical exam at follow-up visit. A COVID-19 questionnaire will be administered at every visit.

Physical Assessments (vital signs, anthropometric measures, brief neurologic exam)

A brief neurologic exam will be conducted at the in-person screening visit. Participants must also be assessed for signs of congestive heart failure, pulmonary, liver or renal disease as contraindications to

metformin. Vital signs including blood pressure and heart rate will be measured. Standing height will be measured using a stadiometer calibrated in cm. Body weight is measured using a balance beam scale calibrated in kg. With the participant standing, measurements are taken to the nearest 0.1 kg of weight with a balance scale and height without shoes to nearest 0.5 cm, to calculate BMI (weight in k/height in m²). Waist circumference (WC) is measured at the level of the umbilicus. Hip circumference (HP) is measured at the level of maximal protrusion of the gluteal muscles. Resting blood pressure (BP) will be measured using an automated oscillometric device; three measurements will be obtained at 1-minute intervals in a seated position after 5 minutes of rest. The average of the 2nd and 3rd measurements will be recorded. Vital signs and anthropometric measures will be repeated at all visits. A full physical exam will be repeated at follow-up visits only in the case of a change in medical history.

Neuropsychological battery

The following battery will be administered at baseline and 6-month visits. For neuropsychological testing, verbatim instructions for administration and specific scoring guidelines will be available. All instruments in the neuropsychological battery are commonly used, validated, published instruments. Non-verified or unpublished instruments are not used in this research study. All tests are validated in English and Spanish. We will use different versions of the tests when available (e.g., different word lists) to account for learning effects. The following is an expanded description of the neuropsychological battery:

- Total Recall Score of the Free and Cued Selective Reminding Test (FCSRT). The FCSRT is a 16-item word list with visual and auditory presentation that uses semantic cuing to facilitate encoding and retrieval. The test has a score range of 0 to 48.
- Paragraph Recall on the Logical Memory Ila (episodic memory): Free recall of one short story that consists of 25 bits of information will be elicited immediately after it is read aloud to the participant and again after approximately 30-minute delay. The total bits of information from the story that are recalled immediately (maximum score = 25) and after the delay interval (maximum score = 25) are recorded. The delay score (0-25 story units) will be used in the composite and also for the inclusion criteria.
- Digit-Symbol Substitution Test: The Digit Symbol Substitution test is a subset from the WAIS-R. The test consists of 110 small blank squares presented in seven rows with one of nine numbers (1-9) randomly printed directly above each blank square. A “key” is printed above the rows of blank squares. The “key” pairs numbers 1 through 9 with an unfamiliar symbol. The participant must work as fast as possible for 90 seconds. The measure of interest is number of squares filled in correctly within the time limit (maximum raw score = 110).
- Mini Mental Status Exam (MMSE). The MMSE scale evaluates orientation, memory, attention, concentration, naming, repetition, comprehension, and ability to create a sentence and to copy two overlapping pentagons. The MMSE is scored as the number of correctly completed items with a lower score indicative of poorer performance and greater cognitive impairment. The total score ranges from zero (worse) to 30 (perfect).
- Trail-Making Test, Part A: This test of visuo-perceptual ability, attention and speed consists of 25 circles distributed over a white sheet of 8 1/2" X 11" paper that are numbered. The participant is instructed to connect the circles with a pencil line as quickly as possible all numbers in an ascending order (e.g., 1 to 2; 2 to 3; etc.). The participant's performance is judged in terms of the time (in seconds) required to complete the task and by the number of errors of commission and omission. The time to complete the trial will be the measures of interest.
- Trail-Making Test, Part B: This test of visuo-perceptual ability, attention and set-shifting ability consists of 25 circles distributed over a white sheet of 8 1/2" X 11" paper that either are numbered

(1 through 13) or contain letters (A through L). The participant is instructed to connect the circles with a pencil line as quickly as possible while alternating between numbers and letters in an ascending order (e.g., A to 1; 1 to B; B to 2; 2 to C). The participant's performance is judged in terms of the time (in seconds) required to complete the task and by the number of errors of commission and omission. The time to complete the trial will be the measures of interest. Trail-Making Test, Part B is available in multiple forms of equal difficulty for purposes of repeated evaluations.

- Functional abilities:
 - ADCS-ADL-PI: The ADCS-ADL-PI was developed in the ADCS Prevention Instruments Trial. The participant and study partner separately rate the participant's performance of 18 IADL tasks over the past 2 months. Questions about use of technology (e.g., computers and cell phones) are included. Responses for each IADL include improved IADL performance (fewer errors, faster completion, less need to refer to notes or instructions), no change ('as well as usual'), various levels of impaired performance, and non-performance.
 - Clinical Dementia Rating (CDR). The CDR is a clinical scale that rates the severity of dementia as absent, questionable, mild, moderate, or severe (CDR score of 0, 0.5, 1, 2, or 3, respectively). The score is based on interviews with the participant and study partner, using a structured interview that assesses six domains: memory, orientation, judgment and problem solving, community affairs, home and hobbies, and personal care. The ratings of degree of impairment obtained on each of the six categories of function are synthesized into one global rating of dementia (ranging from zero to 3), with more refined measure of change available by use of the Sum of Boxes (CDR-SB). Reliability and validity have been established, as has high inter-rater reliability.
- Memory Complaint Questionnaire (MAC-Q): The MAC-Q consists of six items. The first five items relate to specific situations that are frequently reported as troublesome for those with declining memory, and the last item broadly measures overall self-perceived memory decline.
- Mild Behavioral Impairment Checklist (MBI-C): the MBI-C is a rating scale for neuropsychiatric symptoms in a pre-dementia population. It has items in 5 domains: decreased motivation, emotional dysregulation, impulse dyscontrol, social inappropriateness, and abnormal perception or thought content. The MBI inquires about the presence of symptoms in these domains (yes, no) and their severity (mild=1, moderate=2, severe=3). It has 34 items in the 5 domains (maximum score =102). The MBI-C is administered to the study partner.
- Geriatric Depression Scale (GDS): We will administer the 15 item GDS at all visits to assess depressive symptoms. The GDS has 15 yes/no questions assessing depressive symptoms.

Brain imaging

- Magnetic resonance imaging (MRI). We will acquire MP-RAGE and FLAIR imaging according to ADNI2 specifications appropriate to site hardware and operating system. In addition, a Fast T2 Spin-Echo image will be acquired according to site hardware and operating system specifications for evaluation of MRI infarction and to exclude hemorrhage. Standard 2D sequence gradient echo imaging will be acquired to assess micro-hemorrhages as will multi-directional DTI to assess white matter integrity. These latter two image sequences will be standardized according to available hardware and operating systems and may be used for secondary analyses at a future date. The maximum imaging time will be 60 minutes. Following scan acquisition, the data are transferred to a PACS for clinical review of potentially significant incidental findings.

- Amyloid PET: Amyloid PET imaging will be obtained using ¹⁸F-florbetaben. ¹⁸F-florbetaben will be injected as 8.1 mCi, with image acquisition 90-110 min post injection (following CT or transmission scan) as 4 x 5 min frames.
- Tau PET: Tau PET acquisition will entail injection of 5 mCi of MK-6240 with imaging from 90-110 min after CT or transmission scan.¹³⁶

All brain imaging must be completed before study intervention is initiated. To this end, a window of 2 months is allowed between enrollment and commencing titration of study drug to complete brain imaging procedures. For Brain MRI site qualification, a brain MRI with all sequences will be conducted on a volunteer, reviewed from an existing study, or evaluated by the MRI protocol based on the instructions provided during the study setup.

Plasma biomarkers

The plasma AD biomarkers will be measured using the commercially available ultrasensitive single-molecule array (Simoa™) assays.¹³⁷ We will ship frozen plasma aliquots for these procedures at the end of data collection. Compared to the more commonly used ELISA methods, the Simoa™ assays provide high sensitivity and precision, while eliminating the matrix interferences.¹³⁸ Tau, Aβ40, Aβ42 will be assayed together using a multiplex assay (Human Neurology 3-Plex Total). The Simoa™ Human Neurology 3-Plex Total Tau assay uses a combination of monoclonal antibodies that react with both normal and phosphorylated epitopes in the midregion of the molecule yielding an assay that is specific to all tau isoforms. With a mean range of 2.28-109 pg/mL, the lower limit of detection for tau is 0.02 pg/mL, the reproducibility coefficient of variation (CV) is 8.5% and repeatability CV is 7.7%.^{102,137} The Simoa Aβ40 and Aβ42 assays target the N-terminus of beta amyloid and different C-terminus detection antibodies specific to Aβ40 and Aβ42. Aβ42 (mean range: 0-400 pg/mL) has a lower limit of detection of 0.019-0.034 pg/mL, a reproducibility CV=7.5% and repeatability CV=6.7%.^{137,139-141} Aβ40 (mean range: 0-800 pg/mL) has a lower limit of detection of 0.16 pg/mL, a reproducibility CV=5.1% and repeatability CV=3.5%.^{98,141,142} A separate NFL test will be run using the ultrasensitive Simoa™ assay (mean range: 34.7-51.0 pg/mL and lower limit of detection of 0.97 pg/mL, CV=4.3%).^{106,143} Isolation and detection of single enzyme molecules using femtolitre-sized reaction chambers, known as Simoa™. This method detects the target at low concentrations by ensuring that the fluorophores are confined to small volumes, and hence, the concentration of fluorescently labeled target is high. The antibodies are conjugated to magnetic particles utilizing a standard EDC (1-ethyl-3-(3-dimethylaminopropyl) carbodiimide hydrochloride) coupling procedure. In the first step of the assay, antibody coated paramagnetic capture beads, biotinylated detection antibodies, and samples are combined, during which target molecules present in the sample are captured by the capture beads and labeled with the biotinylated detection antibodies. After washing, a conjugate of streptavidin-β-galactosidase (SβG) is mixed with the capture beads where SβG bound to the biotin, resulting in enzyme labeling of captured target molecules. Following a second wash, the capture beads are resuspended in a resorufin β-D-galactopyranoside (RGP) substrate solution and transferred to the Simoa™ array disc for detection. All samples will be diluted 4-fold for Aβ42 and 8-fold for Aβ40 using a proper sample diluent (PBS containing carrier protein and detergent) for measurement. Given the rapid advance in the field of plasma AD biomarkers,¹¹¹ other biomarkers developed using the Simoa™ platform or other methods may replace or be added to those mentioned above.

Cognitive diagnoses

Cognitive diagnosis will be examined for inclusion and exclusion purposes and will also be examined as an exploratory outcome. For cognitive diagnosis transitions (i.e., conversion from MCI to dementia), an adjudication panel at the CCMC will conduct a meeting to arrive at a consensus regarding diagnosis at the

end of the study. This panel will be comprised of investigators [name], [name], and [name]. During the meeting, information of all the cognitive, functional and other clinical information of the participants will be presented, blind to study allocation. Evidence of cognitive deficits (based on the neuropsychological scores), evidence of impairment in social or occupational function (as assessed by the functional measures), and evidence of cognitive and social-occupational function decline will be the criteria used for the diagnosis of dementia.

8.2 SAFETY AND OTHER ASSESSMENTS

General questionnaires. We will collect demographic data including date of birth, sex, education, ethnic and racial group, and country of origin.¹⁴⁴ We will measure depressive symptoms with the Geriatric Depression Scale¹⁴⁵. Medical history (e.g., diabetes) and medications will be collected with questionnaires we currently use for other studies.

COVID-19 questionnaire. The questionnaire includes questions about history of COVID-19, positive testing for coronavirus, symptoms and sequelae including memory problems, reinfection, and vaccination. A history of COVID-19 will be examined as a covariate and modifier.

Laboratory tests. All laboratory tests will be conducted under fasting conditions. Screening (BMP, HbA1c, lipids, hepatic profile, CBC, RPR, B12 levels, TSH) will be conducted at the central laboratory at the Center for Advanced Laboratory Medicine (CALM) at Columbia. BMP, HbA1c, hepatic profile, lipids, B12 levels, and CBC will be repeated at each visit for safety purposes. TSH and RPR will not be repeated at the follow-up visits. APOE will be genotyped (ϵ 2, ϵ 3, and ϵ 4 alleles) by LGC genomics (Beverly, MA; <http://www.lgcgroup.com>) using single nucleotide polymorphisms (SNPs) rs429358 and rs7412. APOE- ϵ 4 will be examined as a covariate and potential modifier. At the end of the study, we will conduct the following laboratory tests in stored samples to examine the impact of the intervention on intermediate outcomes: Insulin levels will be measured using a solid-phase chemiluminescent enzyme immunoassay (Immulite, Diagnostic Products Co, Los Angeles, CA). Inflammatory markers will include hsCRP, serum Amyloid A, IL-6, IL-8, IL-1B, TNFa, WBC, MCP-1 will be measured using ELISA (Diagnostic Systems Laboratories, Inc., Webster, Texas). We will use the American Diabetes Association criteria for HbA1c to diagnose diabetes (HbA1c 6.5% or greater).¹⁴⁶ We will calculate the homeostatic model assessment (HOMA)¹⁴⁷ using glucose (from the BMP) and insulin values as a measure of insulin resistance.

Adverse events. Gastrointestinal symptoms and development of contraindications to metformin will be queried. Reported symptoms will be further evaluated for severity and duration until they resolve. SAEs will be collected and reported on SAE CRF pages.

Measures used for screening. The Clinical Dementia Rating sum of boxes (CDR/CDRsob)¹⁴⁸ will be used primarily for aMCI inclusion criteria but will be assessed at every visit. The Logical Memory II subscale from the Wechsler Memory Scale-Revised will be used for establishing early and late MCI criteria.¹⁴⁹ The MMSE will also be used to establish entry criteria.

8.3 ADVERSE EVENTS AND SERIOUS ADVERSE EVENTS

8.3.1 DEFINITION OF ADVERSE EVENTS (AE)

Adverse events

Adverse event (AE) means any untoward medical occurrence associated with the use of an intervention in humans, whether or not considered intervention related. An AE can therefore be any undesirable sign,

symptom or medical condition occurring after starting IP, even if the event is not considered to be related to the pharmaceutical product. An AE can arise with any use of the drug (e.g., off-label use, use in combination with another drug) and with any route of administration, formulation, or dose, including an overdose (21 CFR 312.32 (a)). Headache, dizziness, lightheadedness, and gastrointestinal upset are AEs that will be specifically questioned about during phone calls and study visits.

8.3.2 DEFINITION OF SERIOUS ADVERSE EVENTS (SAE)

An AE is considered "serious" if, in the view of either the investigator or sponsor, it results in any of the following outcomes:

- Death
- A life-threatening adverse event that places the participant at immediate risk of death at the time of the event as it occurred.
- Inpatient hospitalization or prolongation of existing hospitalization
- A persistent or significant incapacity or substantial disruption of the ability to conduct normal life functions, or a congenital anomaly/birth defect.
- Important medical events that may not result in death, be life-threatening, or require hospitalization may be considered serious when, based upon appropriate medical judgment, they may jeopardize the participant and may require medical or surgical intervention to prevent one of the outcomes listed in this definition. This determination is based on the opinion of either the investigator or sponsor.

The following hospitalizations are not considered SAEs:

- Visits to the emergency room or other hospital department lasting less than 24 hours that do not result in admission (unless considered an "important medical event" or a life-threatening event);
- Elective surgery planned before or after signing consent;
- Medical/surgical admissions other than remedying ill health state that were planned before study entry. Appropriate documentation is required in these cases;
- Admissions encountered for another life circumstance that have no bearing on health status and require no medical/surgical intervention (e.g., lack of housing, economic inadequacy, caregiver respite, family circumstances, administrative reason).

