8.3.4 TIME PERIOD AND FREQUENCY FOR EVENT ASSESSMENT AND FOLLOW-UP

Participants will have assessments including phlebotomy for safety laboratory every 6 months including baseline, 6-months, 12-months, and 18-months visits. In addition, participants will have monthly calls for monitoring of adverse events between visits. The safety laboratory tests will include complete blood count, basic metabolic panel, hepatic panel, and vitamin B12 (cobalamin). Cobalamin testing will allow to assess whether participants develop cobalamin deficiency and anemia, which could be due to metformin, or contraindications to metformin use such as hepatic insufficiency and severe renal insufficiency.

At each study visit, the investigator will inquire about the occurrence of AE and SAEs since the last visit. All AEs and SAEs will be captured on the appropriate eCRF. All AEs and SAEs occurring while on study drug

will be documented appropriately regardless of relationship. All AEs and SAEs will be followed to adequate resolution.

Any medical condition that is present at the time that the participant is screened will be considered as baseline and not reported as an AE. However, if the study participant's condition deteriorates at any time during the study, it will be recorded on the appropriate eCRF (e.g., AE or SAE).

Changes in the severity of an AE or SAE will be documented to allow an assessment of the duration of the event at each level of severity to be performed. AEs and SAEs characterized as intermittent require documentation of onset and duration of each episode.

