8.3.5 ADVERSE EVENT REPORTING

The site investigator is responsible for monitoring the safety of participants enrolled into the study. If an adverse event necessitates modification of study drug dosing, this will be captured on the Dose Change Log eCRF.

All AEs and SAEs occurring from the first day of study enrollment (the day of randomization) to 30 days post last day of study drug dosing will be captured in the AE and SAE eCRF. Unless exempted as described in section 8.3.2, all SAEs, whether or not deemed drug-related or expected, must be reported to the CCC by the investigator or qualified designee **within 24 hours** of first becoming aware of the event. The investigator or qualified designee will enter the required information regarding the SAE into the appropriate module of the eCRF, which will automatically result in distribution of the information to the site-monitoring group, the Safety Event Adjudication Committee, and EMD Serono.

Pregnancy and cancer are not always serious by regulatory definition; however, these events must be submitted to the sponsor within the same time period as an SAE via the EDC.

If the eCRF system is temporarily unavailable, the event, including the investigator-determined causality to study drug should be reported via the back-up paper SAE form to Safety Surveillance. Upon return of the availability of the electronic data capture (EDC) system, the SAE information must be entered onto the eCRF.

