9.4.4 SAFETY ANALYSES

The number of SAEs will be tabulated by type for the entire study sample as well as by treatment group. Any treatment group differences in SAEs enumerated for interim analyses will remain blinded to investigators associated with this study. Unmasked results will be made available only during the closed sessions of DSMB meetings.

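### The SAE exemption for elective surgery also covers operations planned after consent, so some admissions for new or worsened conditions lose SAE status under the hospitalization criterion

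*Protocol*

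**What the plan says.** Section 8.3.2 lists the outcomes that make an adverse event serious. One is "Inpatient hospitalization or prolongation of existing hospitalization". The section then introduces a list of exceptions with "The following hospitalizations are not considered SAEs". The list has four items:

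- Short emergency-room or hospital visits without admission, unless the event is medically important or life-threatening.
- "Elective surgery planned before or after signing consent".
- "Medical/surgical admissions other than remedying ill health state that were planned before study entry", with documentation required.
- Admissions for social or administrative reasons that have no bearing on health.

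Section 8.3.5 carries the list into expedited reporting: "Unless exempted as described in section 8.3.2, all SAEs, whether or not deemed drug-related or expected, must be reported to the CCC", within 24 hours of first awareness. Section 8.3.6 requires immediate reporting of SAEs to the sponsor and sets the limit of 7 calendar days for suspected unexpected serious reactions. For the analysis, section 9.4.4 states: "The number of SAEs will be tabulated by type for the entire study sample as well as by treatment group".

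**The concern.** The words *or after* take away any time limit, and no other condition replaces it. An admission arranged before the trial for a known and stable problem says nothing about the study drug. An admission arranged during the trial, for a problem that appeared or grew worse during the trial, is what the hospitalization criterion is there to pick up. The elective-surgery item treats the two alike.

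SAE status decides which events reach the coordinating center within 24 hours, which can enter the expedited route to regulators, and which are counted by arm in the table that section 9.4.4 names. Hospitalization is also one of the more objective seriousness criteria. If it is switched off for scheduled operations, classification depends more on individual judgment, and two sites may code the same admission differently.

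**Working it through.** The protocol gives no figure on this point, so there is nothing to recompute. The check is a reading of the sections side by side.

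1. **Compare the four exemptions.** The emergency-room item has an exception for important or life-threatening events. The item on other planned admissions is limited both in time (planned before study entry) and in purpose (not to remedy ill health). The last item is limited to admissions without bearing on health. Only the elective-surgery item lacks any limit on timing, purpose or the state of the condition. It also leaves the time limit in the next item with little effect on elective surgical admissions.

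2. **Take a case through the text.** A participant free of a condition at screening develops it at month 8 and is admitted for a scheduled operation at month 10.
   - Section 8.3.1: the condition arose after the start of study drug, so it is an adverse event.
   - Section 8.3.2, criterion: it led to inpatient hospitalization, so it would be serious.
   - Section 8.3.2, exemption: the surgery is elective and was planned after consent, so the hospitalization does not count.
   - Section 8.3.5: the exempted event falls outside the 24-hour rule.
   - Section 8.3.6: the immediate report and the 7-day route apply to serious events, so neither is triggered.
   - Section 9.4.4: the event is not in the SAE count by arm.

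3. **Look for other routes to SAE status.** The condition is still serious if it is life-threatening or incapacitating. Section 8.3.2 also says "Important medical events that may not result in death, be life-threatening, or require hospitalization may be considered serious", on medical judgment, and that clause mentions the need for surgical intervention. Some of these cases will be recovered in this way, but not automatically.

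4. **Look at what is recorded regardless.** Sections 8.3.4 and 8.3.5 capture all adverse events from randomization to 30 days after the last dose. Section 8.3.3.5 requires causality, and section 8.3.3.6 expectedness, for adverse events in general, so neither depends on SAE status. Section 8.3.5 sends cancer to the sponsor on the SAE timeline whether or not it is serious.

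5. **Set the limits of the affected group.** Under section 8.3.4, a condition present at screening is baseline and not an adverse event unless it deteriorates. Surgery for a stable baseline condition is therefore not an SAE, with or without the exemption. The group affected consists of elective inpatient operations, planned after consent, for new or worsened conditions, where no other seriousness criterion is judged to apply.

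**The case against.** The strongest reply is that this is a narrow wording point with several safeguards around it, and much of that stands. Urgent and emergency operations are not exempt. The exemption removes a hospitalization, not the underlying adverse event, which is recorded and assessed and can be serious on other grounds. Section 8.3.8 has investigators ask at visits about hospitalizations and surgeries that require holding the drug, and sends events above set thresholds to the DSMB. Section 10.1.6 gives the DSMB access to all study data. The committee deciding on phase III works from the unblinded trial data (section 9.4.10), not only from the SAE table. The rule is the same in both blinded arms, and the efficacy endpoint is untouched. A statistical analysis plan may add adverse-event tables, so their absence from section 9.4.4 is no defect.

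Three stronger readings are tempting, and the documents do not support them:

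- **That on-study operations are never reported or tabulated as SAEs.** Non-elective operations remain SAEs, and elective ones can be serious under another criterion.
- **That section 8.3.2 contradicts section 8.3.4.** Section 8.3.4 says that "if the study participant's condition deteriorates at any time during the study, it will be recorded on the appropriate eCRF (e.g., AE or SAE"). An adverse-event entry satisfies that sentence, and it concerns conditions present at screening.
- **That the loss can be counted.** If one assumed 2 to 5% of participants per year, then 326 × 1.5 years = 489 person-years, and 489 × 0.02 = 9.8 to 489 × 0.05 = 24.5 operations. The rate has no source in the protocol. The product also includes surgery for stable baseline conditions and ignores the annual loss to follow-up of about 10% assumed in section 9.2.2.

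The safeguards do not remove the defect. They leave the event in the database as a non-serious adverse event, whereas the hospitalization criterion alone would have made it an SAE.

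**Conclusion.** The point holds in a limited form. Followed literally, section 8.3.2 withholds SAE status under the hospitalization criterion from elective inpatient surgery planned after consent for a condition that is new or worsened on study. Unless another criterion is judged to apply, such events may be missing from the 24-hour and expedited reports and from the SAE counts by arm. They are not lost from the adverse-event data.

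The size cannot be estimated from the documents, and nothing in them suggests that the arms would be affected differently. The conclusion assumes that sites apply the exemption as worded. If some sites already report these admissions as SAEs, the consequence is inconsistent classification instead of uniform omission. It is a cheap improvement to safety ascertainment and does not threaten the primary analysis.

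**What to change.** Limit the item in section 8.3.2 to elective surgery planned before signing consent for a condition that has not worsened since. Surgery first planned after consent for a new or worsened condition is then assessed under the ordinary hospitalization criterion. A short note that surgery for a stable baseline condition is not an adverse event, in line with section 8.3.4, would avoid needless forms.

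Then query surgical admissions already in the EDC and reclassify where needed. The dose-change log is a practical starting point: section 2.3.1 cautions participants to stop study drug the day before any surgery, and section 7.1 has every discontinuation recorded there. Adverse-event entries should be searched too, because participants already off drug may have no log entry.

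The cost is one line of protocol text with its IRB review, a one-off query, and a modest number of additional SAE forms, most of them probably unrelated to study drug.
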